#### "Expedited" prenatal sequencing

An alternative to the prenatal diagnostic flow described above permits prenatal sequencing to be performed in parallel with the CMA, i.e. before the fetus is confirmed as CMA negative. This diagnostic workflow is at the discretion of the study research team and participants will be considered enrolled once they have signed the study consent and parental samples have been collected. If the CMA is negative or unrelated to the fetal anomaly, the case will continue to be part of the prenatal sequencing group and included in the analyses. In pregnancies in which the CMA result is found to be pathogenic or likely pathogenic (and presumed causal of the anomaly), sequencing will be discontinued or if already completed the results will be recorded and reported to the family in the appropriate manner. The karyotype/CMA results will be recorded; however, follow-up of the pregnancy through delivery will not take place, these participants will not be included in the analyses and not contribute to the sample size.

#### 4.2.2 Unsequenced prenatal group

The prospective unsequenced prenatal group will include participants that decline invasive testing and those that plan to have invasive testing but decline sequencing (Figure 1). For participants that plan to have invasive testing but decline sequencing, enrollment into the study will occur after the clinical karyotype/CMA results are confirmed negative and the participant signs the prenatal unsequenced consent. Participants that decline invasive testing will be enrolled at the time of diagnosis of the fetal anomaly and they sign the unsequenced prenatal group consent. Women from this group who later elect invasive testing are not eligible to enroll in the prenatal sequencing group but will be included in the unsequenced prenatal analyses if the karyotype and CMA are confirmed negative or non-causal.

Postpartum genetic testing (karyotype and CMA) and genomic sequencing may be performed at the discretion of the clinical care team as part of routine care. Continued follow-up of the pregnancy and 1-year postpartum period will not take place if a pathogenic or likely pathogenic causal CMA is identified prior to neonatal discharge.

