# 3 Study Design

# 3.1 Design Summary

This multicenter, observational cohort study will evaluate prenatal sequencing among pregnancies with fetal structural anomalies recruited at university based medical centers and evaluated at four genetic laboratories. A total of 1,100 pregnancies with fetal structural anomalies and meeting eligibility criteria will be enrolled into the study. Of these, 750 will undergo prenatal genomic sequencing (prenatal sequencing group) and the remaining 350 pregnancies will not have any prenatal genomic sequencing (unsequenced prenatal group). Enrollment of pregnancies with an isolated nuchal translucency measurements  $\geq$  3.5 mm and < 4.5 mm without evidence of cystic hygroma will be restricted to 5% within each group (sequenced and unsequenced) and isolated estimated fetal weight <5th %ile also will be restricted to 5% for each group (sequenced and unsequenced).

The prenatal sequencing group will be used to determine the frequency of pathogenic, likely pathogenic, and uncertain genomic variants identifiable by sequencing and the relative yield of sequencing. The prenatal sequencing group will be compared with the unsequenced prenatal group (prospective and retrospective) to evaluate health care management, health care utilization and cost, and perinatal outcomes. The prenatal sequencing group will be compared with the prospective unsequenced prenatal group to evaluate psychosocial needs of pregnant couples. Mothers, fathers and infants will be followed through 1 year postpartum for participants enrolled prospectively.

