#### 3.2.1.2 Exclusion Criteria

- 1. Imminent delivery planned (within 3 weeks of enrollment) as sequencing results would not be available prior to delivery
- 2. Prenatal sequencing or planned prenatal sequencing performed outside of the study. Gene panels may be performed prior to enrollment but the results must be known and negative to be eligible (positive or unknown results are an exclusion).

- 3. Maternal or paternal age less than 18 years old
- 4. Proven infectious, teratogenic, or other genetic cause of fetal anomaly
- 5. For twin gestation, anomalies in both fetuses (NT, IUGR, or structural anomaly)
- 6. Monochorionic diamniotic (MCDA) and monochorionic monoamniotic (MCMA) twins as well as higher-order multifetal gestations
- 7. Planned termination of the fetus or intrauterine fetal demise (IUFD)
- 8. Unavailable blood or saliva samples from both genetic parents prior to sequencing
- 9. Parental unwillingness to participate in 1 year postnatal follow-up
- 10. Language barrier (non-English or Spanish speaking)
- 11. Previous consent to the unsequenced prenatal group or enrollment in a previous pregnancy

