# 3.2.2 Prospective unsequenced prenatal group

#### 3.2.2.1 Inclusion Criteria

- 1. Fetus identified by ultrasound and/or MRI with at least one of the following:
  - a. One or more suspected major structural anomalies (Appendix A)
  - b. A nuchal translucency measurement of  $\geq$  3.5 mm and < 4.5 mm without evidence of cystic hygroma
  - c. A fetus less than 24 weeks 0 days gestation with normal anatomy and sonographically estimated fetal weight <5th %ile without maternal hypertension, type I diabetes, or other maternal disorders known to alter fetal growth
- 2. Declined prenatal sequencing
- 3. Singleton gestation or dichorionic diamniotic (DCDA) twin gestation.
- 4. Gestational age less than 36 weeks, 0 days

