#### 3.2.2.2 Exclusion Criteria

- 1. Prenatal or postnatal (prior to neonatal discharge) CMA with pathogenic or likely pathogenic variants that are related to the prenatal ultrasound finding
- 2. Maternal or paternal age less than 18 years old
- 3. Proven infectious, teratogenic, or other genetic cause of fetal anomaly
- 4. Positive prenatal NIPT screening for trisomy 21, 18 or 13. Positive 22q11.2 prenatal NIPT testing with consistent ultrasound findings is also an exclusion.
- 5. For twin gestation, anomalies in both fetuses (NT, IUGR, or structural anomaly)
- 6. Monochorionic diamniotic (MCDA) and monochorionic monoamniotic (MCMA) twins as well as higher-order multifetal gestations.
- 7. Planned termination of the fetus or intrauterine fetal demise (IUFD)
- 8. Unable to consent both genetic parents
- 9. Parental unwillingness to participate in 1 year postnatal follow-up

10. Language barrier (non-English or Spanish speaking)

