#### 3.2.3.1 Inclusion Criteria

- 1. Fetus identified by ultrasound and/or MRI with at least one of the following:
  - a. One or more suspected major structural anomalies (Appendix A)
  - b. A nuchal translucency measurement of  $\geq$  3.5 mm and < 4.5 mm without evidence of cystic hygroma
  - c. A fetus less than 24 weeks 0 days gestation with normal anatomy and sonographically estimated fetal weight <5th %ile without maternal hypertension, type I diabetes, or other maternal disorders known to alter fetal growth
- 2. Did not pursue prenatal sequencing
- 3. Singleton gestation or dichorionic diamniotic (DCDA) twin gestation.
- 4. Gestational age less than 36 weeks, 0 days at date study-specified anomalies first diagnosed

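### The prospective control rules do not remove a pregnancy that has clinical prenatal sequencing, although section 3.1 defines the unsequenced group as having none

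*Combined protocol and SAP*

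**What the plan says.** All references are to version 1.8 of the protocol in the combined document.

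- **Section 3.1** defines the comparison group: "the remaining 350 pregnancies will not have any prenatal genomic sequencing (unsequenced prenatal group".
- **Section 3.2.1.2** lists, as an exclusion for the sequenced group, "Prenatal sequencing or planned prenatal sequencing performed outside of the study". Gene panels before enrolment are tolerated, but "the results must be known and negative to be eligible (positive or unknown results are an exclusion".
- **Section 3.2.2.1** requires of prospective controls "Declined prenatal sequencing". It does not say whether the study's offer or any sequencing is meant.
- **Section 3.2.2.2** has ten exclusions for prospective controls. None names sequencing outside the study. The nearest is item 3: "Proven infectious, teratogenic, or other genetic cause of fetal anomaly".
- **Section 3.2.3.1** requires of retrospective controls "Did not pursue prenatal sequencing".
- **Section 4.2.1** lets parents who refuse at the consent stage be offered the unsequenced group.
- **Section 4.2.2** enrols controls who refuse invasive testing when the anomaly is diagnosed. It then says "Women from this group who later elect invasive testing are not eligible to enroll in the prenatal sequencing group", but that they "will be included in the unsequenced prenatal analyses if the karyotype and CMA are confirmed negative or non-causal". Its next paragraph mentions clinical genomic sequencing of controls only after birth.
- **Section 5.3** names one exclusion from the group comparison: a causal CMA finding made before the newborn leaves hospital.
- **Table 2** collects clinically ordered genetic tests in the unsequenced group, later sequencing included.

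**The concern.** The comparison is meant to show what prenatal sequencing results do to charges, perinatal outcomes and parents' wellbeing. A control whose fetus is sequenced clinically before delivery has received that exposure. If she is analysed as unsequenced, the contrast is likely to shrink, and the group no longer matches its definition in section 3.1.

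The protocol itself treats clinical sequencing as a live possibility. The amendment log entry of 19 April 2019 explains the sequenced group's exclusion on the ground that clinical sequencing could change interpretation and outcomes. That reasoning applies equally to the controls, but the prospective controls were not given the same rule. They are also the only controls in the psychosocial and 12-month comparisons, so any gap there is not diluted by the retrospective controls.

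**Working it through.** **Step 1: follow a prospective control through the rules.** Take a woman who refuses invasive testing, enrols when the anomaly is diagnosed, later has an amniocentesis with an unremarkable CMA, and then has a clinical exome before delivery.

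- Inclusion (3.2.2.1): she declined sequencing when she enrolled, so she qualifies.
- Exclusions (3.2.2.2): none refers to sequencing. Item 3 may apply if the exome proves a cause. It does not apply if the result is negative or uncertain.
- Later invasive testing (4.2.2): the stated condition concerns karyotype and CMA only, and she meets it.
- Analysis (5.3): only a causal CMA removes a pregnancy, and she has none.

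No operational rule takes her out, while section 3.1 says the group contains no such pregnancy. The case of a woman who refuses the study's offer because she will be sequenced clinically turns on what declining means, which is not stated. A retrospective control would not pass, because her criterion looks back over the pregnancy.

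**Step 2: reproduce the plan's power figure.** Inputs from section 5.1: mean charge $277,902, SD $389,484, lognormal; 500 sequenced and 300 controls; mean ratio 0.80; two-sided alpha 0.05; stated power 80%.

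- CV = 389,484 / 277,902 = 1.4015
- Log-scale SD = sqrt(ln(1 + 1.4015²)) = 1.0424
- Effect = |ln 0.80| = 0.2231
- SE = 1.0424 × sqrt(1/500 + 1/300) = 0.0761
- Power = Φ(0.2231/0.0761 − 1.960) = 83.4%

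The noncentral t gives 83.3%. The Mann-Whitney test, which section 5.3 allows for non-normal data, gives 81.7% using its relative efficiency of 3/π. The stated 80% is therefore reproduced, slightly conservatively.

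**Step 3: illustrate dilution.** The documents give no crossover rate. Assume that a share c of all 300 analysed controls was sequenced prenatally, has the full 0.80 effect and otherwise has average charges. The log effect becomes (1 − c) × 0.2231, and the apparent ratio is exp(−(1 − c) × 0.2231).

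| c (assumed) | Controls | Apparent ratio | Power, log scale | Power, Mann-Whitney | Power if these controls are removed, log scale |
|---|---|---|---|---|---|
| 0% | 0 | 0.800 | 83.4% | 81.7% | 83.4% |
| 2% | 6 | 0.804 | 81.9% | 80.2% | 83.0% |
| 5% | 15 | 0.809 | 79.5% | 77.7% | 82.2% |
| 10% | 30 | 0.818 | 75.1% | 73.2% | 80.9% |
| 20% | 60 | 0.836 | 65.0% | 63.0% | 77.8% |

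A ratio of arithmetic means, 0.80 / ((1 − c) + 0.80c), gives nearly the same: 0.808 at 5% and 0.816 at 10%.

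Only prospective controls can be affected. If half of the 300 were prospective (an assumption, as no split is given), then 5% or 10% of all controls means 10% or 20% of the prospective ones.

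**The case against.** The strongest reply is that no rule keeps a prenatally sequenced control. The sentence in 4.2.2 is about later invasive testing and waives nothing else. Clinical sequencing of controls is foreseen only after birth, and section 3.1 points against keeping such a pregnancy. On its plain words, a woman planning clinical sequencing has not declined sequencing. Much of this stands. A reader might infer that the protocol deliberately retains sequenced controls; the documents do not say so. They are silent, and the definition and the working rules do not meet.

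A reader might also infer that a control with a prenatal molecular diagnosis certainly stays in. That is not supported, because item 3 of 3.2.2.2 may catch a proven cause. But item 3 does not say whether it applies after enrolment, whereas CMA has explicit post-enrolment rules. If it does apply, diagnosed controls leave while diagnosed pregnancies in the sequenced group stay, which is a further reason to state the rule.

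Finally, a reader might conclude that the study falls below its stated power. The table cannot show that. The crossover rate and the full effect are assumed, and the share is spread over all 300 controls although retrospective controls are already covered. Crossovers may also differ in suspected genetic disease, so pure dilution is likely but not established.

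**Conclusion.** The gap is real and confined to the prospective controls. Section 3.1 defines them as having no prenatal genomic sequencing, but the eligibility, follow-up and analysis rules do not remove one who is sequenced clinically before delivery, except possibly where a cause is proven.

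The likely consequence is dilution of the charge and perinatal contrasts, and of the psychosocial and 12-month contrasts that use prospective controls alone. Its size cannot be derived from the documents. Under the stated assumptions, crossover in 5% or 10% of all analysed controls would move a ratio of 0.80 to 0.81 or 0.82 and take log-scale power from 83% to about 80% or 75%. The inconsistency itself does not depend on those figures.

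**What to change.** 1. In 3.2.2.2, add the sequenced group's exclusion of outside or planned outside prenatal sequencing at enrolment, with the same gene-panel wording as 3.2.1.2.
2. In 3.2.2.1, state that having declined sequencing covers clinical as well as study sequencing.
3. In 4.2.2 and 5.3, use the genetic-test data in Table 2 to flag prospective controls who had genomic sequencing before delivery. The date of each test is needed, because Table 2 does not separate prenatal from postpartum results.
4. Report the group comparisons with and without the flagged controls. A known-negative gene panel alone should not count as a breach of section 3.1, which speaks of genomic sequencing; the sequenced group also accepts such panels.

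The cost is one criterion, one clarification and one sensitivity analysis on data already collected. For controls already enrolled, only the flag and the paired analyses can help. A few controls may be lost; in the illustration, removing 5% or 10% leaves log-scale power at 82.2% or 80.9%. Removing pregnancies after enrolment may select on suspected genetic disease, which is why both results should be shown.

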#### 4.2.3 Retrospective unsequenced prenatal group

The retrospective unsequenced prenatal group will include participants from the screening log who did not actively decline enrollment and are otherwise eligible. Participants will be considered enrolled at the time of diagnosis of the fetal anomaly.

#### 4.3 Baseline Data Collection

In addition to data collected for eligibility and consent, the following information will be obtained at enrollment from either medical record review or participant interview:

- Maternal and paternal: age, race, ethnicity, education, income, household composition, religion, religiosity, number of children, and family history
- Maternal medical and psychiatric history including maternal history of disorders with teratogenic risk (e.g. diabetes, teratogen exposure including medications, diseases during pregnancy (e.g. CMV, Zika)
- Obstetrical history including

- Clinical estimated date of delivery and type of conception
- Pre-procedure ultrasounds including date and detailed information on anomaly(ies)
- Number of prior pregnancies and gestational age of delivery
- Unexplained infertility
- Twin gestation
- Family history of learning disabilities, genetic disorders, congenital anomalies, stillbirths or infant deaths, significant medical problems, fetal/child structural or growth findings, consanguinity, deafness and psychiatric illnesses.
- Prenatal screening and diagnostic test results; rubella immunity status

A copy of de-identified imaging, karyotype and CMA reports will be transferred to the DCC for all enrolled patients.

# 4.4 Sequencing Methods

Prenatal sequencing will be performed for patients in one of the four laboratories, i.e. the Institute of Genomic Medicine (IGM) at Columbia University Medical Center, New York Genome Center (NYGC), in the Human Genome Sequencing Center CLIA certified Clinical Laboratory (HGSC-CL) at Baylor College of Medicine, and at the High Throughput Sequencing Facility at the University of North Carolina Chapel Hill.

Sequencing will be performed on an Illumina NovaSeq 6000 system. All positive sequencing results will be confirmed using Sanger sequencing and reported by a CLIA certified laboratory. It is possible that non-parentage (maternity or paternity) may be suspected through initial genomic analysis. If there is suspicion that the parent of the fetus is not the genetic parent, further analysis of the genomic data will be suspended and the family will be informed they are not eligible for study participation. This approach will be addressed during the informed consent process.

Data quality control, including alignment, variant calling, filtering and prioritization will be performed using best practices refined at the local institutions.

#### 4.5 Variant Evaluation and Return of Results

All candidate variants will first be evaluated locally at each site by a team including the site PI who is a board certified clinical geneticist, a study genetic counselor, a variant curation scientist, and a board-certified molecular geneticist with clinical genome sequencing experience to determine candidate variants relevant to the clinical phenotype. Factors used in this evaluation include the ACMG classification of the variant, whether its inheritance mode is consistent with the clinical condition, and the extent of phenotypic overlap with previously reported cases. Initially, candidate variants will be reported in the coding regions only; however it is anticipated that over the course of the study this may change to also incorporate reporting in non-coding regions.

Compelling variants in novel genes that are not yet disease associated will be classified as variants of uncertain significance (VUS) with the qualification that they are in "genes of uncertain clinical significance (GUS)". For compelling variants in known disease genes that have not yet been associated with this disease phenotype (also classified as VUS), in-house databases will be checked for similar variants, automated PubMed alerts will be set-up to be notified of new publications, and tools such as GeneMatcher will be used to help find other individuals with variants in the same gene. To build consensus in interpretation, the local Variant Interpretation teams will have video conferences on which uncertain results will be discussed.

Any pathogenic, likely pathogenic or VUS finding that are reported to the participant will be confirmed by Sanger sequencing. For all reportable results, a copy of the Sanger confirmation report and additional relevant information as applicable will be prepared by the local team and returned to the clinical study genetic counselor who will share the result with the ordering MFM/OB physician and place it in the electronic medical record (EMR). The ordering MFM/OB physicians and the study genetic counselor will report the results to the family and discuss the implications for clinical care. Study clinical geneticists will be available for consultation. Results will also be available to the neonatal care team for use after delivery. A copy of the de-identified report will be transferred to the DCC for all patients.

Local site requirements will dictate the reporting (if at all) of Sanger-confirmed ACMG secondary or other incidental findings of the parents and fetus. Findings in the fetus that may impact treatment decisions on the newborn will be reported immediately.

Carrier status for Mendelian disorders in either parent will be reported according to the local site requirements.

Parents will be formally informed of negative fetal sequencing results only if testing is performed in a CLIA approved laboratory.

# 4.6 Study Procedures

Women who are enrolled prospectively will be followed from screening through 12 months postpartum unless a pathogenic or likely pathogenic causal CMA is reported prenatally or postnatally prior to neonatal discharge. Women who are enrolled retrospectively will be followed from screening through delivery discharge. For twin gestations, neonatal data will only be collected for the fetus with the anomaly. Data will be collected at the following time points:

**Table 2. Summary of Data Collection** 

Two weeks after discussion of study results or 4 weeks after enrollment for the unsequenced prenatal group	Maternal and paternal psychosocial survey
Delivery and neonatal care	
 
Pregnancy complications & delivery outcomes
 
Neonatal phenotype and outcomes
 
Coordinator and physician review of medical records to assess change in management (sequencing group only)
 
Results of clinical care ordered genetic testing for unsequenced group including karyotype/CMA and any subsequent sequencing
 
Reports of healthcare utilization and charges from admission for delivery to discharge (maternal)
 
Healthcare utilization and charges from delivery until discharge or death (neonatal)
 

One month post discharge (prospective only)	Maternal and paternal psychosocial survey
12 months postpartum (prospective only)	
 
Maternal and paternal psychosocial survey
 
Infant weight and length, genetic testing post discharge, and healthcare utilization by maternal self-report
 

	Ages and Stages questionnaire (ASQ-3)
--	---------------------------------------

Neonatal phenotypes will be re-evaluated within one week of birth and infant phenotypes at 12 months to identify additional clinical features. If significant new clinical findings are discovered, the sequencing variants will be re-evaluated immediately by the local team and any new diagnoses confirmed and reported by the study staff to the neonatologist, pediatrician, or other appropriate care provider who will report this to the family in concert with the study coordinator. A copy of de-identified genetic reports (CMA and/or sequencing) will be transferred to the DCC for all enrolled patients in the unsequenced group.

